5.3.2.3 Sampling of faeces

Faeces will be collected at time points or in intervals as indicated in the [Flow Chart](#):

- To determine total [¹⁴C]-radioactivity
- To investigate the metabolic profiling of BI 1291583 (to be reported separately)

A blank sample will be taken within approximately 48 hours prior to drug administration. If several samples are available, the sample closest to drug administration will be used for analyses.

Faeces samples collected after administration of BI 1291583 (C-14) until release criteria are met are planned to be used for determination of [¹⁴C]-radioactivity. Samples to be used for metabolic profiling will be selected according to the levels of radioactivity in each faeces sample interval. For faeces samples to be discarded (see footnote 13 and 14).

All stools will be collected continuously in portions up to 336 hours after drug administration. All stool portions will be taken quantitatively at the time-points depicted in the [Flow Chart](#). The weight of the faeces and the exact times of faeces collection will be recorded in the eCRF.

If subjects are to collect faeces during the ambulatory phase of the study (see Section [3.1](#) for release criteria), subjects are to collect faeces at home within 24 h intervals before admission to once-weekly in-house collection intervals. Home collection intervals are (if applicable): Days 20-21, 27-28, 34-35, and 41-42. All faeces samples (including home collection, if

Proprietary confidential information © 2023 Boehringer Ingelheim International GmbH or one or more of its affiliated companies

applicable) will be shipped [REDACTED]. If faeces is collected during in-house collection interval, this faeces sample will be used for analysis and the respective home collection faeces sample has to be discarded. If no faeces is collected in the subsequent in-house collection interval (no defecation), faeces collected at home will be used instead for analysis.

[figure not shown]
For a detailed description of faeces sample preparation, sample storage, labelling, and sample shipment refer to the laboratory manual.

[figure not shown]
5.3.2.4 Collection of vomit

If vomiting occurs within 24 hours after drug administration the vomit will be collected to calculate the weight and determine the [¹⁴C]-radioactivity levels. For a description of vomit sample preparation, sample storage, labelling, and sample shipment refer to the laboratory manual.

5.3.2.5 Further investigation

After analysis, blood, plasma, urine, faeces and vomit (if applicable) samples may be used for further methodological investigations (e.g. for stability testing, assessment of metabolites) or to address Health Authority questions regarding the results/methodology. However, only data related to the analyte and/or its metabolite(s) will be generated by these additional investigations. The trial samples will be discarded after completion of the additional investigations but not later than 5 years after the CTR has been archived.

5.4 ASSESSMENT OF BIOMARKERS

Not applicable.

5.5 BIOBANKING

Not applicable.

5.6 OTHER ASSESSMENTS

Not applicable.

5.7 APPROPRIATENESS OF MEASUREMENTS

All measurements performed during this trial are standard measurements and will be performed in order to monitor subjects' safety and to determine pharmacokinetic parameters in an appropriate way. The scheduled measurements will allow monitoring of changes in vital signs, standard laboratory values, and ECG parameters that might occur as a result of administration of trial medication. The safety assessments are standard, are accepted for evaluation of safety and tolerability of an orally administered drug, and are widely used in clinical trials. The pharmacokinetic parameters and measurements outlined in Section [5.3](#) are generally used assessments of drug exposure in human mass-balance trials.

6. INVESTIGATIONAL PLAN

6.1 VISIT SCHEDULE

Exact times of measurements outside the permitted time windows will be documented. The acceptable time windows for screening and the end of trial examination are provided in the [Flow Chart](#).

Study measurements and assessments scheduled to occur 'before' trial medication administration on Day 1 are to be performed and completed within a 4 h-period prior to the trial drug administration.

If not stated otherwise in the [Flow Chart](#), the acceptable deviation from the scheduled time up to 1 h post-dose \pm 1 min.

After 1 h post-dose there is a 10% time window (for safety assessments except safety lab) and a 5% time window (for blood sampling PK, metabolic profiling, safety lab) of elapsed time since drug administration.

If scheduled in the [Flow Chart](#) at the same time as a meal, blood sampling, vital signs, and 12-lead ECG recordings have to be done first. Furthermore, if several measurements including venipuncture are scheduled for the same time, venipuncture should be the last of the measurements due to its inconvenience to the subject and possible influence on physiological parameters.

For planned blood sampling times and urine / faeces collection intervals, refer to the [Flow Chart](#). While these nominal times should be adhered to as closely as possible, the actual sampling times will be recorded and used for the determination of pharmacokinetic parameters.

If beginning or end of a urine/faeces collection interval and a blood sample are scheduled for the same time point, urine/faeces collection should be done first, with withdrawal of the blood sample as closely to the planned time point as possible.

If a subject misses an appointment, it will be rescheduled if possible. The relevance of measurements outside the permitted time windows will be assessed no later than at the Report Planning Meeting.

6.2 DETAILS OF TRIAL PROCEDURES AT SELECTED VISITS

6.2.1 Screening period

After having been informed about the trial, all subjects will provide written informed consent in accordance with GCP and local legislation prior to enrolment in the trial.

For information regarding laboratory tests (including drug and virus screening), ECG, vital signs, and physical examination, refer to Sections [5.2.1](#) to [5.2.5](#).

6.2.2 Treatment period

Each subject is expected to participate in one treatment period (Visit 2).

Proprietary confidential information © 2023 Boehringer Ingelheim International GmbH or one or more of its affiliated companies

On Day -1 of the treatment period study participants will be admitted to the trial site and kept under close medical surveillance until discharge from the trial site on Day 15. In the morning of Day 15, the subjects will then be allowed to leave the trial site after formal assessment and confirmation of their fitness.

Until release criteria (see Section [3.1](#)) have been reached, subjects will take part in the 24-h collection intervals of urine and faeces. For these additional 24 h collection intervals, subjects will be admitted to the trial site on Days 21, 28, 35, and 42. One day later, on Days 22, 29, 36, and 43, respectively, subjects will be discharged from the trial site after formal assessment and confirmation of their fitness.

Within 24 h before each once-weekly in-house collection interval, subjects are to collect faeces at home (beginning of home collections on Days 20, 27, 34, and 41). Faeces collected in these 24 h home-collection intervals will be used for analysis in case no defecation occurs in the subsequent 24 h in-house collection interval. E.g., if no defecation occurs in in-house collection interval Day 21-22, faeces of home-collection interval Day 20-21 will be used for analysis. If, however, faeces are collected in the subsequent 24 h in-house collection interval, faeces collected at home will be discarded. Once release criteria are reached, home collections will be stopped.

Irrespective of whether release criteria have been met or not after collection interval Days 42-43, no further collections are planned. For details on time points and procedures for collection of plasma, whole blood, urine and faeces samples for PK analysis and mass balance assessment, refer to [Flow Chart](#) and Section [5.3.2](#).

The safety measurements performed during the treatment period are specified in Section [5.2](#) of this protocol and in the [Flow Chart](#). AEs and concomitant therapy will be assessed continuously from obtaining subject's written informed consent until the end of trial examination. For details on times of all other trial procedures, refer to the [Flow Chart](#).

6.2.3 Follow-up period and trial completion

For AE assessment, laboratory tests, recording of ECG and vital signs, and physical examination during the follow-up period, see Section [5.2](#).

Subjects who discontinue treatment before the end of the planned treatment period should undergo the EoS Visit.

If needed in the opinion of the investigator, additional visits may be scheduled after the EoS Visit for continued safety monitoring.

All abnormal values (including laboratory parameters) that are assessed as clinically relevant by the investigator will be monitored using the appropriate tests until a return to a medically acceptable level is achieved. (S)AEs persisting after a subject's EoS Visit must be followed until they have resolved, have been sufficiently characterised, or no further information can be obtained.

7. STATISTICAL METHODS AND DETERMINATION OF SAMPLE SIZE

7.1 NULL AND ALTERNATIVE HYPOTHESES

This is a phase I, non-randomised, open-label, single-dose, single-arm study to investigate human ADME of BI 1291583 administered to healthy male subjects. No confirmatory analysis will be conducted for this study. Data will be reported with descriptive statistics only. The following standard descriptive statistical parameters will be displayed in summary tables of continuous variables:

- N number of non-missing observations
- Mean arithmetic mean
- SD standard deviation
- Min minimum
- Median median
- Max maximum

For concentration data as well as for all PK parameters the following descriptive statistics will additionally be calculated:

- CV arithmetic coefficient of variation
- gMean geometric mean
- gCV geometric coefficient of variation

For PK parameters the following descriptive statistics will additionally be calculated:

- P10 10th percentile
- Q1 1st quartile
- Q3 3rd quartile
- P90 90th percentile

Tabulations of frequencies for categorical data will include all possible categories and will display the number of observations in a category as well as the percentage (%) relative to the respective treatment group.

Further details may be provided in the TSAP.

7.2 PLANNED ANALYSES

7.2.1 General considerations

7.2.1.1 Analysis sets

Statistical analyses will be based on the following analysis sets:

- Treated set (TS): The treated set includes all subjects who were treated with at least one dose of trial drug. The treated set will be used for safety analyses.
- Pharmacokinetic parameter analysis set (PKS): This set includes all subjects in the treated set (TS) who provide at least one PK endpoint that was defined as primary or

Proprietary confidential information © 2023 Boehringer Ingelheim International GmbH or one or more of its affiliated companies

secondary and was not excluded due to a protocol deviation relevant to the evaluation of PK or due to PK non-evaluability (as specified in the following subsection 'Pharmacokinetics'). Thus, a subject will be included in the PKS, even if he/she contributes only one PK parameter value for one period to the statistical assessment. Descriptive and model-based analyses of PK parameters will be based on the PKS.

Descriptions of additional analysis sets may be provided in the TSAP.

Adherence to the protocol will be assessed by the trial team. Important protocol deviation (IPD) categories will be suggested in the IPD specification file. IPDs will be identified no later than in the Report Planning Meeting, and the IPD categories will be updated as needed.

7.2.1.2 Pharmacokinetics

The pharmacokinetic parameters listed in Section [2.1](#) and [2.2.2](#) for drug BI 1291583 and its metabolites will be calculated according to the relevant BI internal procedures.

Plasma, urine, faeces, and vomit (as applicable) concentration data and parameters of a subject will be included in the statistical pharmacokinetic (PK) analyses if they are not flagged for exclusion due to a protocol deviation relevant to the evaluation of PK (to be decided no later than in the Report Planning Meeting) or due to PK non-evaluability (as revealed during data analysis, based on the criteria specified below). Exclusion of a subject's data will be documented in the CTR.

Important protocol deviations may be

- Incorrect trial medication taken, i.e. the subject received at least one dose of trial medication the subject was not assigned to
- Incorrect dose of trial medication taken
- Use of restricted medications

Plasma, urine and faeces concentrations and/or parameters of a subject will be considered as non-evaluable, if for example

- The subject experienced emesis that occurred at or before two times median t_{max} of the respective treatment (Median t_{max} is to be determined excluding the subjects experiencing emesis). For collection of vomit see Section [5.3.2.4](#).
- A pre-dose concentration (in plasma) is $>5\%$ C_{max} value of that subject
- Missing samples/concentration data at important phases of PK disposition curve

Plasma, urine, faeces, and vomit (if applicable) concentration data and parameters of a subject which are flagged for exclusion will be reported with its individual values but will not be included in the statistical analyses. Descriptive and inferential statistics of PK parameters will be based on the PKS.

[figure not shown]
Only concentration values within the validated concentration range and actual sampling times will be used for the calculation of pharmacokinetic parameters. Concentrations used in the pharmacokinetic calculations will be in the same format provided in the bioanalytical report, (that is, to the same number of decimal places provided in the bioanalytical report).

7.2.2 Primary endpoint analyses

The primary endpoints (refer to Section [2.1.2](#)) will be calculated according to the relevant BI internal procedures. The analysis will be descriptive in nature. To avoid underestimation of the total recovery of [¹⁴C], the excretion during the non-sampling phase of the study will be estimated using linear interpolation between the observed 24-h sampling periods before and after the non-sampling period for urine and feces respectively.

7.2.3 Secondary endpoint analyses

The secondary endpoints (refer to Section [2.1.3](#)) will be calculated according to the relevant BI internal procedures and will be descriptive in nature.

7.2.5 Safety analyses

Safety will be analysed based on the assessments described in Section [2.2.2.2](#). All treated subjects (TS, refer to Section [7.2](#)) will be included in the safety analysis. Safety analyses will be descriptive in nature and based on BI standards. No hypothesis testing is planned.

For all analyses, the treatment actually administered (= treatment at onset) to the subject will be used (any deviations from the treatment will be discussed in the minutes of the Report Planning Meeting).

Treatments will be compared in a descriptive way. Tabulations of frequencies/proportions will be used to evaluate categorical (qualitative) data, and tabulations of descriptive statistics will be used to analyse continuous (quantitative) data.

Measurements (such as ECG, vital signs, or laboratory parameters) or AEs will be assigned to treatments (see Section [4.1](#)) based on the actual treatment at the time of the measurement or on the recorded time of AE onset (concept of treatment emergent AEs). Therefore, measurements performed or AEs recorded prior to first intake of trial medication will be assigned to the screening period, those between first trial medication intake and end of REP (see Section [1.2.2](#)) will be assigned to the treatment period. Events occurring after the REP but prior to next intake or end of trial termination date will be assigned to 'follow-up'. In case of two or more treatments, the follow-up will be summarized according to the previous treatment. These assignments including the corresponding time intervals will be defined in detail in the TSAP. Note that AEs occurring after the last per protocol contact but entered before unblinding the trial will be reported to Pharmacovigilance only and will not be captured in the trial database.

Additionally, further treatment intervals (analysing treatments) may be defined in the TSAP in order to provide summary statistics for time intervals, such as combined treatments, on-

Proprietary confidential information © 2023 Boehringer Ingelheim International GmbH or one or more of its affiliated companies

treatment totals, or periods without treatment effects (such as screening and follow-up intervals). The final TSAP is signed/approved 10 days before database lock at the latest.

Adverse events will be coded using the Medical Dictionary for Regulatory Activities (MedDRA). Frequency, severity, and causal relationship of AEs will be tabulated by treatment, system organ class, and preferred term. SAEs, AESIs (see Section [5.2.6.1](#)), and other significant AEs (according to ICH E3) will be listed separately.

Previous and concomitant therapies will be presented per treatment group without consideration of time intervals and treatment periods.

Laboratory data will be compared to their reference ranges. Values outside the reference range will be highlighted in the listings. Additionally, differences from baseline will be evaluated.

Vital signs or other safety-relevant data will be assessed with regard to possible on-treatment changes from baseline.

Relevant ECG findings will be reported as AEs.

7.2.6 Interim analyses

No interim analysis is planned.

7.3 HANDLING OF MISSING DATA

7.3.1 Safety

It is not planned to impute missing values for safety parameters.

7.3.2 Pharmacokinetics

Handling of missing PK data will be performed according to the relevant BI internal procedures.

PK parameters that cannot be reasonably calculated based on the available drug concentration-time data will not be imputed.

7.4 RANDOMISATION

The trial will not be randomised, thus this section is not applicable.

7.5 DETERMINATION OF SAMPLE SIZE

For this exploratory study, no prospective calculations of statistical power have been made. The sample size of 8 subjects has been selected to provide at least 6 evaluable subjects. This is considered sufficient information to assess the main objectives of this trial.

8. INFORMED CONSENT, TRIAL RECORDS, DATA PROTECTION, PUBLICATION POLICY, AND ADMINISTRATIVE STRUCTURE

The trial will be carried out in compliance with the protocol, the ethical principles laid down in the Declaration of Helsinki, in accordance with the ICH Harmonized Guideline for Good Clinical Practice (GCP), relevant BI SOPs, the EU regulation 536/2014, and other relevant regulations. Investigators and site staff must adhere to these principles. Deviation from the protocol, the principles of ICH GCP or applicable regulations will be treated as 'protocol deviation'.

Standard medical care (prophylactic, diagnostic, and therapeutic procedures) remains the responsibility of the subject's treating physician.

The investigator will inform the sponsor immediately of any urgent safety measures taken to protect the trial subjects against any immediate hazard, as well as of any serious breaches of the protocol or of ICH GCP.

The Boehringer Ingelheim transparency and publication policy can be found on the following web page: trials.boehringer-ingelheim.com. The rights of the investigator and of the sponsor with regard to publication of the results of this trial are described in the investigator contract. As a general rule, no trial results should be published prior to finalisation of the CTR.

The terms and conditions of the insurance coverage are made available to the investigator and the subjects and are stored in the ISF.

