3.3.5 Replacement of subjects

In case some subjects do not complete the trial, subjects may be replaced if considered necessary to reach the objective of the trial. Subjects who withdraw or are withdrawn from treatment or assessments because of a drug-related adverse event will not be replaced. The Clinical Trial Leader together with the Trial Pharmacokineticist and the Trial Statistician are to decide, if and how many subjects will be replaced. The total number of replacements may not exceed 1/3 of the total number of evaluable subjects anticipated to complete the trial. A replacement subject will be assigned a unique trial subject number.

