8.3.1 Source documents

In accordance with regulatory requirements, the investigator should prepare and maintain adequate and accurate source documents and trial records for each trial subject that include all observations and other data pertinent to the investigation. Source data as well as reported data should follow the 'ALCOA principles' and be attributable, legible, contemporaneous, original, and accurate. Changes to the data should be traceable (audit trail).

Data reported on the CRF must be consistent with the source data or the discrepancies must be explained.

Before providing any copy of subjects' source documents to the sponsor, the investigator must ensure that all subject identifiers (e.g., subject's name, initials, address, phone number, and social security number) have properly been removed or redacted to ensure subject confidentiality.

If the subject is not compliant with the protocol, any corrective action (e.g. re-training) must be documented in the subject file.

For the CRF, data must be derived from source documents, for example:

- Subject identification: gender, year of birth (in accordance with local laws and regulations)
- Subject participation in the trial (substance, trial number, subject number, date subject was informed)

Proprietary confidential information © 2023 Boehringer Ingelheim International GmbH or one or more of its affiliated companies

- Dates of subject's visits, including dispensing of trial medication
- Medical history (including trial indication and concomitant diseases, if applicable)
- Medication history
- AEs and outcome events (onset date [mandatory], and end date [if available])
- SAEs (onset date [mandatory], and end date [if available])
- Concomitant therapy (start date, changes)
- Originals or copies of laboratory results and other imaging or testing results, with proper documented medical evaluation (in validated electronic format, if available)
- ECG results (original or copies of printouts)
- Completion of subject's participation in the trial (end date; in case of premature discontinuation, document the reason for it, if known)

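### Does a replacement rule worded for non-completers undermine the target of 6 evaluable subjects?

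*Protocol*

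**What the plan says.** Protocol 7.5 makes no power calculation and says: "The sample size of 8 subjects has been selected to provide at least 6 evaluable subjects". Section 3.3 takes the figure of 6 from cited guidance on human ADME studies.

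Section 3.3.5 governs replacement: "In case some subjects do not complete the trial, subjects may be replaced if considered necessary to reach the objective of the trial". Subjects who leave "because of a drug-related adverse event will not be replaced". The Clinical Trial Leader, the Trial Pharmacokineticist and the Trial Statistician decide together whether and how many to replace. The cap is one third of the evaluable subjects expected to complete.

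Section 7.2.1.2 opens its list of examples with: "Plasma, urine and faeces concentrations and/or parameters of a subject will be considered as non-evaluable, if for example". The first is: "The subject experienced emesis that occurred at or before two times median" tmax. The others are a plasma pre-dose concentration above 5% of Cmax, and missing samples at important phases of the disposition curve. Data are excluded for a relevant protocol deviation or "due to PK non-evaluability (as revealed during data analysis, based on the criteria specified below".

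Section 7.2.1.1 admits a subject to the PKS "even if he/she contributes only one PK parameter value for one period to the statistical assessment". SAP 7.4.1 keeps every parameter value not flagged for exclusion, and SAP 7 lists the individual values of all subjects.

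**The concern.** The target is counted in evaluable subjects and the replacement rule in non-completers. None of the three examples in 7.2.1.2 requires a subject to leave the trial. A man who vomits early and attends every visit is a completer, so on a strict reading 3.3.5 gives no route to replace him, yet his excretion fractions might be set aside. A completer with a lost stool portion is in a similar position, and no listed example names incomplete excreta collection.

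PKS membership does not fill the gap, because a single plasma Cmax is enough to enter it. Six subjects in the PKS need not mean six usable mass balances. Protocol 8.3.1 also seems to separate completion from early discontinuation, since the records must show completion of "participation in the trial (end date; in case of premature discontinuation, document the reason for it, if known".

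At stake is the number of usable mass balances. No hypothesis test is affected.

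**Working it through.** **Inputs from the documents.** 8 subjects dosed and at least 6 evaluable (7.5), so the buffer is 8 − 6 = 2. The replacement cap (3.3.5) is 6/3 = 2, or 8/3 = 2.67 on the full number, so two whole subjects either way. No loss rate is given; every rate below is an assumption, and subjects are treated as independent.

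**Is 8 for 6 sensible?** Rounding 6/(1 − loss rate) up gives 7 at 10% loss, 8 at 15%, 20% and 25%, and 9 at 30%. So 8 fits an allowance of up to 2/8 = 25%.

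**The buffer alone.** Suppose every loss is a non-evaluable completer with probability q, and none can be replaced. Then P(at least 6) = Σ C(8,k) q^k (1 − q)^(8−k), for k = 0 to 2. At q = 0.10 this is 0.4305 + 0.3826 + 0.1488 = 0.962. At 5%, 15% and 20% it is 0.994, 0.895 and 0.797. If two replacements were open to any loss (10 subjects, at least 6 evaluable), the values at 5%, 10%, 15% and 20% are 0.9999, 0.998, 0.990 and 0.967.

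**A mix of losses.** Let d = 5% drop out (replaceable) and c complete but be non-evaluable. The 8 subjects are multinomial, with up to 2 replacements at the same rates. P(fewer than 6 evaluable):

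| c (assumed) | Only drop-outs replaced | Both kinds replaced |
|---|---|---|
| 1% | 0.0002 | 0.0002 |
| 2% | 0.0009 | 0.0003 |
| 3% | 0.0022 | 0.0006 |
| 5% | 0.0080 | 0.0016 |
| 10% | 0.0468 | 0.0099 |
| 15% | 0.1238 | 0.0328 |

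If a replacement who drops out may himself be replaced, the middle column at 5%, 10% and 15% becomes 0.0074, 0.0453 and 0.1214. The right-hand column assumes that every non-evaluable completer is recognised while dosing is still possible, so it is a best case.

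**Emesis and the excretion fractions.** Section 7.2.1.2 speaks of concentrations and/or parameters and points to 5.3.2.4, where radioactivity in vomit is measured. Whether early vomiting removes a subject's excretion fraction is therefore open, not settled. The rule also needs the median tmax of the treatment, computed without the subjects who vomited, which site records of vomiting do not supply.

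**The lost portion.** A portion holding more than 100 − 90 = 10 points of dose puts the 90% release criterion out of reach. That does not decide who completes: 3.1 requires released subjects to return for blood sampling as well. If the value stays in, a loss of 10, 20 or 30 points lowers the mean recovery of 8 subjects by 10/8 = 1.25, 20/8 = 2.5 or 30/8 = 3.75 points. A replacement rule does not remove that effect, and the individual value is listed.

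**The case for a change.** The strongest case for a change is that the buffer covers two losses and a replacement rule exists for the third; that is where the wording fails. Section 3.3.5 even mentions evaluable subjects in its cap, so it recognises the concept but does not use it as the trigger. The proviso about reaching the trial's objective reads as a limit on the non-completion condition, not a second way in. Two or three sentences would align the two sections, and a definition based on completeness of collection would not select on the recovery achieved.

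The textual part stands: evaluable is undefined for the excretion fractions, and a strict reading of 3.3.5 leaves out completers. The rest is weaker.

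- Section 7.5 never cites replacement, so the sample size does not rest on it.
- Completion is not defined either. The line in 8.3.1 is an item in a list of source data.
- Section 4.3 lets non-compliant subjects be removed, which would make some of them non-completers.
- The list in 7.2.1.2 is open. SAP 6.2 places the trial's deviation categories, and their effect on analysis sets, in the DV domain specification, and protocol 7.2.1.1 refers to an IPD specification file. Neither file is among the documents reviewed, so one can say only that no excreta-completeness criterion appears in the protocol or SAP.
- Non-evaluability found during data analysis may come to light after dosing has ended, when no trigger helps.

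**Conclusion.** The mismatch in wording is real, but it is missing detail and not a fault in the sample size. Dosing 8 to obtain 6 is arithmetically reasonable and covers the first two losses from any cause. Beyond that, the effect depends wholly on assumed rates. It is negligible at 1% to 3% non-evaluable completers (0.0002 to 0.0022, with 5% drop-out). It becomes appreciable only near 10% to 15% (0.047 to 0.124), rates for which the documents give no support and which seem high for a design with in-house collection to Day 15.

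Following the plan as written produces no wrong result. The analysis is descriptive, exclusions are documented, all individual values are listed, and a reader can count the usable mass balances. Widening the trigger would have a cost: it could mean giving radiolabelled drug to further healthy volunteers, and 4.1.6 plans no re-supply. Leaving the decision to the trial leader, pharmacokineticist and statistician is a fair trade-off in a trial of this size. They can agree what evaluable means for the excretion fractions when a case arises, and no later than the Report Planning Meeting. No change to the plan is needed.
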